7.3.4 Monitoring

Clinical site auditing is conducted to ensure that the rights of human subjects are protected, that the study is implemented in accordance with the protocol and regulatory requirements, and that the quality and integrity of study data and data collection methods are maintained. Auditing for this study will be performed by the **City of Hope Office of Clinical Trials Auditing and Monitoring (OCTAM)**.

The site Investigator/Institution will permit the study auditors and appropriate regulatory authorities direct access to the study data and to the corresponding source data and documents to verify the accuracy of this data. The Investigator will allocate adequate time for such monitoring activities. The Investigator will also ensure that the monitor or other compliance or quality assurance reviewer is given access to all the above noted study-related documents and study related facilities (e.g. pharmacy, diagnostic laboratory, etc.), and has adequate space to conduct the monitoring visit.

Details of clinical site monitoring are documented in the **OCTAM SOP** that is provided as a supplement to this document. This document specifies the frequency of monitoring, monitoring procedures, the level of clinical site monitoring activities (e.g., the percentage of subject data to be reviewed), and the distribution of monitoring reports. Staff from **OCTAM** will conduct monitoring activities and provide reports of the

findings and associated action items in accordance with the details described in the **SOP**. Documentation of monitoring activities and findings will be provided to the site study team, the site PI, study PI, and the COH DSMC.

7.3.5 Quality Assurance

The City of Hope Clinical Research Information Support will provide support for this multi-center trial as detailed in the COH DCC Operations Plan provided as a supplement to this document.

7.3.6 City of Hope Data and Safety Monitoring Committee

This is a risk level 3 study as defined in the [City of Hope Institutional Data and Safety Monitoring Plan](#). This determination was made because this study is a Phase IIA trial that is IND Exempt.

The DSMC is a multidisciplinary committee charged with overseeing the monitoring of safety of participants in clinical trials, and the conduct, progress, validity, and integrity of the data for all clinical trials that are sponsored by City of Hope. The committee is composed of clinical specialists with experience in oncology and who have no direct relationship with the study. The committee reviews the progress and safety of all active research protocols that are not monitored by another safety and data monitoring committee or board.

The Study Principal Investigator is required to submit periodic status reports (the PMT report) according to the guidelines outlined in the [City of Hope Institutional Data and Safety Monitoring Plan](#). The PMT report will be submitted to the COH DSMC **every six months** from the date of activation.

The COH Data and Safety Monitoring Committee (DSMC) will review and monitor toxicity and accrual data from this trial. The DSMC will review up-to-date participant accrual; summary of all adverse events captured via routine and expedited reporting; a summary of deviations; any response information; monitoring reports, and summary comments provided by the study team. Other information (e.g. scans, laboratory values) will be provided upon request. For Phase I studies, a Phase I Tracking Log will be utilized and reviewed by the DSMC to monitor data and safety for dose escalation. A review of outcome results (response, toxicity and adverse events) and factors external to the study (such as scientific or therapeutic developments) is discussed, and the Committee votes on the status of each study.

Information that raises any questions about participant safety will be addressed with the Principal Investigator, statistician and study team. The PMT report and DSMC recommendations will be circulated to all participating sites for submission to their IRBs, in accordance with NIH guidance.

7.4 Novartis Adverse Event Reporting Guidelines

To ensure patient safety, every SAE, regardless of suspected causality, occurring after the patient has provided informed consent and until at least 30 days after the patient has stopped study treatment must be reported to Novartis within 24 hours of learning of its occurrence.

Any SAEs experienced after this 30 days period should only be reported to Novartis if the investigator suspects a causal relationship to the study treatment. Recurrent episodes, complications, or progression of the initial SAE must be reported as follow-up to the original episode within 24 hours of the investigator receiving the follow-up information. An SAE occurring at a different time interval or otherwise considered completely unrelated to a previously reported one should be reported separately as a new event.

If the SAE is not previously documented in the Investigator's Brochure or Package Insert (new occurrence) and is thought to be related to the Novartis study treatment, an oncology Novartis Drug Safety and Epidemiology (DS&E) department associate may urgently require further information from the investigator for Health Authority reporting. Novartis may need to issue an Investigator Notification (IN), to inform all investigators involved in any study with the same drug that this SAE has been reported. Suspected Unexpected Serious Adverse Reactions (SUSARs) will be collected and reported to the competent authorities and relevant ethics committees in accordance with Directive 2001/20/EC or as per national regulatory requirements in participating countries.

Pregnancies

To ensure patient safety, each pregnancy in a patient on study treatment must be reported to Novartis within 24 hours of learning of its occurrence. The pregnancy should be followed up to determine outcome, including spontaneous or voluntary termination, details of the birth, and the presence or absence of any birth defects, congenital abnormalities, or maternal and/or newborn complications.

Pregnancy should be recorded on a Clinical Trial Pregnancy Form and reported by the investigator to the oncology Novartis Drug Safety and Epidemiology (DS&E) department. Pregnancy follow-up should be recorded on the same form and should include an assessment of the possible relationship to the Novartis study treatment of any pregnancy outcome. Any SAE experienced during pregnancy must be reported on the SAE Report Form.

Pregnancy outcomes must be collected for the female partners of any males who took study treatment in this study. Consent to report information regarding these pregnancy outcomes should be obtained from the mother.

8. AGENT INFORMATION

[figure not shown]
8.1. Ribociclib

8.1.1. Other Names

Kisqali

8.1.2. Description and Molecular Weight

Structural formula:

Empirical formula: C₂₃H₃₀N₈O

Molecular weight: 434.254272 g/mol

Chemical Name: 7-Cyclopentyl-N,N-dimethyl-2-{[5-(1-piperazinyl)-2-pyridinyl]amino}-7H-pyrrolo[2,3-d]pyrimidin-6-carboxamid

8.1.3. Mechanism of Action

Inhibitor of cyclin-dependent kinase (CDK) 4 and 6. Cyclin D1 and CDK4/6 are downstream of signaling pathways which lead to cellular proliferation. In vitro, ribociclib reduced cellular proliferation of estrogen receptor (ER)-positive breast cancer cell lines by blocking progression of the cell from G1 into S phase of the cell cycle. Treatment of breast cancer cell lines with the combination of ribociclib and antiestrogens leads to decreased retinoblastoma protein (Rb) phosphorylation, resulting in reduced E2F expression and signaling and increased growth arrest compared to treatment with each drug alone. In vitro treatment of ER-positive breast cancer cell lines with the combination of ribociclib and antiestrogens leads to increased cell senescence, which was sustained for up to 6 days following drug removal. In vivo studies using a patient-derived ER-positive breast cancer xenograft model demonstrated that the combination of ribociclib and letrozole increased the inhibition of Rb phosphorylation, downstream signaling and tumor growth compared to each drug alone.[22]

8.1.4. Pharmacokinetics

Absorption:	Compared to a fasted state, oral administration with a high-fat, high-calorie meal has no effect on the rate and extent of absorption of ribociclib.
Distribution: V_d (mean):	1090 L
Protein binding:	~70%
Metabolism:	Extensively hepatic; Major pathways: Oxidation (dealkylation, C and/or N-acetylation), sulfation, cysteine conjugation, glycosylation and glucuronidation.
Bioavailability:	Mean absolute bioavailability: 46%
Half-life elimination:	32 hours
Time to peak:	1 to 4 hours
Excretion:	Feces. 92% of dose recovered within 22 days; feces is the major route of excretion (69%), with 23% recovered in urine.

8.1.5. Human Toxicity

See [Section 6.1.1](#).

8.1.6. Formulation

Ribociclib is supplied as a 600 mg, 400 mg, or 200 mg doses in assorted blister packs. Each film-coated contains 200 mg of ribociclib free base. Ribociclib is supplied as a light greyish violet, round tablet, curved with beveled edge, debossed with “RIC” on one side and “NVR” on the other. Inactive ingredients present in the tablet include: colloidal silicon dioxide, crospovidone, hydroxypropylcellulose, magnesium stearate, and microcrystalline cellulose.

8.1.7. Storage

The blister packs should be stored at 20°C to 25°C (68°F to 77°F); excursions permitted between 15 to 30°C (59 to 86°F).

8.1.8. Preparation

Ribociclib may be repackaged to provide appropriate capsule quantities to participants. Tabs should not be distributed if broken, cracked or otherwise not intact.

8.1.9. Dose and Administration

See [Section 6.2](#).

8.1.10. Supplier

Study drug is being provided by the drug manufacturer, Novartis.

8.1.11. Accountability

The investigator, or a responsible party designated by the investigator, must maintain a careful record of the inventory and disposition of the agent (investigational or free of charge) using the NCI Drug Accountability Record or another comparable drug accountability form.

8.1.12. Destruction and Return

Any unused agent at the end of the study, expired agent, and damaged agent will be destroyed according to institutional policies. **Prior** to the destruction of ribociclib, the DCC should be notified and an acknowledgement to proceed from the DCC should be received. Destruction will be documented in the Drug Accountability Record.

[figure not shown]
8.2 Letrozole

Please refer to the Package Insert for additional details for [letrozole](#) not provided in this section.

8.2.1. Other names

Femara.

8.2.2. Description and Molecular Weight

Structural formula:	
Empirical formula:	C ₁₇ H ₁₁ N ₅
Molecular weight:	285.30 g/mol
Chemical Name:	4-[(4-cyanophenyl)-(1,2,4-triazol-1-yl)methyl]benzonitrile

8.2.3.

Mechanism of Action:

Nonsteroidal competitive inhibitor of the aromatase enzyme system which binds to the heme group of aromatase, a cytochrome P450 enzyme which catalyzes conversion of androgens to estrogens (specifically, androstenedione to estrone and testosterone to estradiol). This leads to inhibition of the enzyme and a significant reduction in plasma estrogen (estrone, estradiol and estrone sulfate) levels. Does not affect synthesis of adrenal or thyroid hormones, aldosterone, or androgens.

8.2.4. Human Toxicity

See [Section 6.1.2](#).

8.2.5. Pharmacokinetics

Absorption:	Rapid and well absorbed; not affected by food
Distribution: V_d :	~1.9 L/kg
Protein binding plasma:	Weak
Metabolism:	Hepatic via CYP3A4 and 2A6 to an inactive carbinol metabolite
Half-life elimination:	Terminal: ~2 days
Time to steady state, plasma	2 to 6 weeks; steady state serum concentrations are 1.5 to 2 times higher than single-dose values
Excretion:	Urine (90%; 6% as unchanged drug, 75% as glucuronide carbinol metabolite, 9% as unidentified metabolites)

8.2.6. Supplier

Letrozole is commercially available.

8.3 Exemestane

Please refer to the Package Insert for additional details for [exemestane](#) not provided in this section.

8.3.2. Other names

Aromasin

8.3.3. Description and Molecular Weight

Structural formula:	
Empirical formula:	C ₂₀ H ₂₄ O ₂
Molecular weight:	296.403 g/mol
Chemical Name:	6-Methylideneandrosta-1,4-diene-3,17-dione

8.3.4. Mechanism of Action

Exemestane is an irreversible, steroidal aromatase inactivator. It is structurally related to androstenedione, and is converted to an intermediate that irreversibly blocks the active site of the aromatase enzyme, leading to inactivation (“suicide inhibition”) and thus preventing conversion of androgens to estrogens in peripheral tissues. Exemestane significantly lowers circulating estrogens in postmenopausal breast cancers where growth is estrogen-dependent.

8.3.5. Human Toxicity

See [Section 6.1.3](#).

8.3.6. Pharmacokinetics

Absorption:	Rapid and moderate (~42%) following oral administration; AUC and C _{max} increased by 59% and 39%, respectively, following a high-fat breakfast compared to fasted state
Distribution:	Extensive into tissues
Protein binding plasma:	90%, primarily to albumin and α_1 -acid glycoprotein
Metabolism:	Extensively hepatic; oxidation (CYP3A4) of methylene group, reduction of 17-keto group with formation of many secondary metabolites; metabolites are inactive
Half-life elimination:	~24 hours
Time to peak:	Women with breast cancer: 1.2 hours

Excretion:	Urine (<1% as unchanged drug, 39% to 45% as metabolites); feces (36% to 48%)
------------	------------------------------------------------------------------------------

8.3.7. Supplier

Exemestane is commercially available.

8.4 Anastrozole

[figure not shown]
Please refer to the Package Insert for additional details for [anastrozole](#) not provided in this section.

8.4.2. Other names

Arimidex

8.4.3. Description and Molecular Weight

Structural formula:

Empirical formula: C₁₇H₁₉N₅

Molecular weight: 293.37 g/mol

Chemical Name: 2-[3-(2-cyanopropan-2-yl)-5-(1,2,4-triazol-1-ylmethyl)phenyl]-2-methylpropanenitrile

8.4.4. Mechanism of Action

Anastrozole is a selective non-steroidal aromatase inhibitor. By inhibiting aromatase, the conversion of androstenedione to estrone, and testosterone to estradiol, is prevented, thereby decreasing tumor mass or delaying progression in patients with tumors responsive to hormones.

8.4.5. Human Toxicity

See [Section 6.1.4](#).

8.4.6. Pharmacokinetics

Onset of estradiol reduction:	70% reduction after 24 hours; 80% after 14 days of daily dosing
-------------------------------	-----------------------------------------------------------------

Duration of serum estradiol reduction:	6 days
Absorption:	Well absorbed; food reduces the rate but not the overall extent of anastrozole absorption
Protein binding plasma:	40%
Metabolism:	Extensively hepatic (~85%) via N-dealkylation, hydroxylation, and glucuronidation; primary metabolite (triazole) inactive
Half-life elimination:	~50 hours
Time to peak, plasma:	~2 hours without food; 2 to 5 hours with food
Excretion:	Feces; urine (urinary excretion accounts for ~10% of total elimination, mostly as metabolites)

8.4.7. Supplier

Anastrozole is commercially available.

9. CORRELATIVE/SPECIAL STUDIES

9.1 Blood Banking (Optional)

With patient permission obtained (via informed consent), blood (10 mL- green top heparin OR lavender top K+EDTA) will be collected at baseline for future mRNA and DNA isolation and stored in order to be banked for future research. Such studies might include genetic testing to determine how genetics influences chemotherapy toxicity. Samples will be stored between -60°C to -90°C at the COH Clinical Immunobiology Correlative Studies Laboratory (CICSL) until future downstream processing.

Collection, Processing, Labeling and Shipping

Refer to [Appendix D1](#) for collection and to [Appendix D2](#) for shipping (non-COH sites only)

10. RIBOCICLIB PHARMACOKINETICS

10.1 Clinical Pharmacology Objectives

To determine average plasma steady-state ribociclib C_{trough} concentrations in patients over the age of 70 years. Further, we will determine the relationship between average plasma C_{trough} and percent decreases in neutrophil and platelet counts in patients. [24]

10.2 Blood Sample Collection

Blood samples will be collected from a peripheral vein or indwelling venous catheter or by venipuncture. At each time point indicated in the table below, peripheral blood will be collected into a single 10 ml green-top tube (sodium or lithium heparin) to prevent blood clotting. Tubes will be inverted several times and then immediately placed on ice for transportation to the Analytical Pharmacology Core Facility (APCF), the processing laboratory.

Blood samples will be collected at the times indicated in table 10.2.1 below. **Patients will be instructed not to take their ribociclib on these days until after they have had their blood drawn in the clinic.**

Table 10.2 Time Points for Blood Sample Collection for PK Studies

Time Point	Cycle	Day	Date (mm/dd/yy)	Time (hr:min)
Pretreatment	1	1*		
C1D8	1	8		
C1D15	1	15		
C2D1	2	1		
C2D8	2	8		
C2D15	2	15		

*All samples to be drawn prior to the dose of ribociclib on that day.

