5.3. Treatment Plan and Agent Administration

Table 5.3: Treatment regimen

Agent	Starting Dose	Frequency of Administration	Route of Administration
Ribociclib	600 mg/ day	Once daily on Days 1-21 of each 28-day cycle	Orally
Aromatase inhibitor	Per package insert	Per treating investigator's discretion during each 28-day cycle	Per package insert

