5.3.1. Ribociclib

Ribociclib should be taken at approximately the same time each day with food. Ribociclib tablets should be swallowed whole.

If applicable, ribociclib may be taken at the same time as endocrine therapy.

If a patient vomits or misses a dose, an additional dose should not be taken that day. The next prescribed dose should be taken at the usual time.

Management and dose modification associated with ribociclib adverse events are outlined in [Section 6.2](#). ribociclib doses missed for toxicity will not be made up during a cycle.

Participants will be supplied with a Pill Diary ([Appendix E](#)) to assess ribociclib compliance.

Ribociclib has been shown to prolong the QT interval in a concentration dependent manner, with mean increase in QTc interval being 22.9 ms (90% CI: 21.6-24.1). Therefore, ECG will be assessed prior to initiation of treatment and patients will only be eligible if QTcF values under <450 msec.

5.3.2. Aromatase inhibitor:

Participants will receive an aromatase inhibitor, according to the package insert and investigator discretion.

Modification in the dose of endocrine therapy due to unacceptable toxicity will occur per treating investigator's discretion.

The type of aromatase inhibitor may be switched at the treating investigator's discretion. Types of aromatase inhibitor includes letrozole, exemestane and anastrozole.

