10.5 Pharmacokinetic Data Analysis Methods

Average plasma C_{trough} will be calculated for each subject and the population results will be summarized using standard statistical methods.

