 - r. Adverse events (AEs) experienced by participants will be collected and recorded from the pre-treatment Cycle 1 Day 1 safety assessments up to 30 days of the last dose of study medication. See [Section 7.0](#) for reporting guidelines). AEs will be recorded by MD on C1D1, C1D15, C2D1, C2D15, and C3D1. AEs will be recorded by RN on C1D8 and C2D8.
 - s. The period for collection, recording and reporting of AEs is extended for participant with ongoing adverse events requiring expeditious reporting (see [Section 7.3](#)).
 - t. Ribociclib pill diary: The participant will be given a pill diary (see [Appendix E](#)) which will be reviewed for adherence. It will **not be a deviation** if the diary is not returned prior to initiation of the subsequent cycle.
 - u. Geriatric Assessment (GA) to be administered either via paper (from PDF supplement) or tablet data entry. Duration for completion is usually between 20 and 40 minutes. [Appendix F](#) details the GA content, but is not for administration.

- v. GA to be administered within seven days of Cycle 1 Day 1 protocol therapy. GA will not be administered for Cycle 2 Day 1.
- w. GA and CT to be performed prior to Cycle 3 (\pm 7 days), then every 3 cycles (\pm 7 days).
- x. Was It Worth It (WIWI) Questionnaire (See [Appendix G](#) for content only but not for administration, a separate PDF can be requested from the lead study team) and Overall Treatment Utility (OTU) Questionnaire (See [Appendix H](#)).
- y. Imaging to be performed within 28 days prior to enrollment.
- z. Post-baseline radionucleotide imaging to be performed only as clinically indicated or to confirm complete response.
 - aa. CT of chest, abdomen, pelvis, any clinically indicated sites of disease, and of bone lesions.
 - bb. Confirmatory scans following documentation of progression or response will not be required; progression/response will be determined based on results of the single time point. See [Section 11.0](#).
 - cc. Refer to [Section 6.2](#) for dose modification/ dose delay guidelines.
 - dd. Medical chart review for disease progression/response will also occur until progression or the initiation of a new therapy at least twice annually or as requested by the lead study team. Post-study new therapy regimens will be collected.

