13.1.5 Secondary Endpoints

1. All toxicities associated with the combinations as measured by NCI CTCAE v.4.0
2. Dose reductions
3. Dose holds
4. Hospitalizations
5. Response as determined by RECIST criteria
6. Progression free survival defined as the time from start of treatment to the first of the following disease events: local/regional/distant recurrence, invasive contralateral breast disease, second primary or death due to any cause
7. Overall survival defined as the time from start of treatment to death due to any cause
8. To determine average plasma steady-state ribociclib C_{trough} concentrations in patients over the age of 70 years

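### A pre-dose draw is accepted as a ribociclib C_trough whatever the time since the previous dose, so evening dosers' values read about 19% to 30% high and late-drawn morning dosers' read low

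*Combined protocol and SAP*

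**What the plan says.** - **Sampling rule.** Section 10.2 tells sites: "Patients will be instructed not to take their ribociclib on these days until after they have had their blood drawn in the clinic". The footnote to Table 10.2 repeats the condition: "All samples to be drawn prior to the dose of ribociclib on that day". Neither gives an interval since the previous dose or a window around it.
- **Dosing.** Table 5.3 has ribociclib taken "Once daily on Days 1-21 of each 28-day cycle", so a trough falls about 24 h after the previous dose. Section 5.3.1 adds: "Ribociclib should be taken at approximately the same time each day with food". Morning or evening is left open, and the diary in Appendix E prints am/pm on every dosing line.
- **What is recorded.** Table 10.2 has columns for the date and time of the sample and none for the last dose. The diary asks for a clock time for each dose, but no section links it to the pharmacokinetic analysis. Under Study Calendar footnote t, it is not a deviation "if the diary is not returned prior to initiation of the subsequent cycle". The protocol asks for last-intake date and time alongside a PK sample only in Table 6.2.2d, for QT prolongation.
- **Use of the values.** Section 13.1.5 lists the endpoint as: "To determine average plasma steady-state ribociclib C_{trough} concentrations in patients over the age of 70 years". Section 10.5 says: "Average plasma C_{trough} will be calculated for each subject and the population results will be summarized using standard statistical methods". Sections 10.1 and 13.4 then relate the trough to percent falls in neutrophil and platelet counts through linear models.

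**The concern.** Drawing before that day's dose is the same as drawing a trough only if the patient doses at about the hour of the clinic visit. A patient who doses at 8 pm and is drawn between 8 am and noon meets Section 10.2 exactly, yet is only 12 to 16 h past the last dose. A patient who usually doses at 8 am, holds the dose as told and is drawn at 2 pm is 30 h past it. Both values enter Section 10.5 as C_trough on the same footing.

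Two analyses are affected. One is a listed secondary endpoint, whose values would depend partly on when patients take their tablets and when the clinic sees them. The other is the trough-versus-counts model, where timing error in the predictor tends to weaken the fitted slope if dosing habit is unrelated to the counts. The primary toxicity endpoint is untouched.

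**Working it through.** The plan gives no target, precision or sample size for C_trough, so there is no stated figure to reproduce.

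**Inputs**
- Half-life 32 h and time to peak 1 to 4 h (Section 8.1.4).
- Dosing interval 24 h on Days 1 to 21 (Table 5.3).
- Sampling on Days 1, 8 and 15 of Cycles 1 and 2 (Table 10.2).
- Assumption: daytime draws, so 12 to 16 h after an evening dose. Clinic hours are not in the documents.
- Assumption: one compartment, steady state.

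**Step 1: one mis-timed sample.** At 12 h and beyond, concentration is on the declining limb, so relative to the 24 h trough

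`C(t)/C(24) = 2^((24 - t)/32)`

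| Hours since dose | Ratio | Error |
|---|---|---|
| 12 | 2^(12/32) = 1.297 | +30% |
| 14 | 2^(10/32) = 1.242 | +24% |
| 16 | 2^(8/32) = 1.189 | +19% |
| 20 | 2^(4/32) = 1.091 | +9% |
| 28 | 2^(-4/32) = 0.917 | -8% |
| 30 | 2^(-6/32) = 0.878 | -12% |

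Adding first-order absorption with a time to peak of 1, 2 or 4 h leaves the 12 to 20 h ratios unchanged to three decimals. For half-lives other than the protocol's (assumption), the errors at 12 and 16 h are +41% and +26% with 24 h, and +19% and +12% with 48 h.

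**Step 2: which samples can be steady-state troughs.**
- Day 8 follows 7 doses: 1 - 2^(-7×24/32) = 0.974 of steady state.
- Day 15 follows 14 doses: 1 - 2^(-14×24/32) = 0.999.
- C1D1 precedes any drug, so it is 0.
- C2D1 comes 8 days (192 h) after the Day 21 dose: 2^(-(192 - 24)/32) = 0.026 of the trough.

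Only C1D8, C1D15, C2D8 and C2D15 qualify. Section 10.5 does not say so. Averaging all six would give (0 + 0.974 + 0.999 + 0.026 + 0.974 + 0.999)/6 = 0.66 of the true trough.

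**Step 3: the cohort mean.** The share of evening dosers is not given. If 20% to 50% dosed in the evening and were drawn at 14 h, they alone would add 0.2 × 24.2% = 4.8% to 0.5 × 24.2% = 12.1%. Late-drawn morning dosers pull the other way. With 25% evening dosers at 14 h and 50% morning dosers at 30 h, 0.25 × 24.2% = 6.1% is cancelled by 0.50 × 12.2% = 6.1%. The sign of the net error cannot be settled from the documents.

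**The case against.** The strongest reply is that this is a descriptive secondary endpoint with no comparator, threshold or decision rule attached. Dose times may also be recoverable: the diary asks for a date and clock time for each dose, and late return does not stop them being used at the end of the study. The eCRFs, including the treatment forms in Table 14.3, and any PK laboratory form are not in the documents, so last-dose time may be captured there. All of that is fair, and it limits the weight of the point. It does not remove it, because no section says that time since dose will be checked or used.

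A reader might infer more than the documents support:
- **That cohort C_trough is biased upward.** This would count evening dosers only. Late-drawn morning dosers read low, and averaging in C1D1 and C2D1 would pull the result well below the true trough.
- **That the error would pass for an age effect.** The background argues that drug handling changes with age, but no section plans a comparison of C_trough with younger patients.
- **That morning dosers will be sampled near peak, because the diary carries no hold notice for PK days.** That needs a departure from Section 10.2. The diary's silence does not show that the instruction is not given.
- **That dose time exists only in the diary.** This cannot be established without the case report forms.

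**Conclusion.** The point holds at the level of the individual value. Following Section 10.2 to the letter lets a sample at 12 to 16 h count as a trough, about 30% to 19% too high, and one at 30 h count as a trough, about 12% too low. These sizes rest on the protocol's 32 h half-life, a one-compartment steady-state model and assumed daytime clinic hours. The net cohort bias is unknown in size and sign. The timing error also enters the predictor in the neutrophil and platelet models; the documents do not allow that effect to be sized.

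This is more than missing detail, because full compliance with the stated rule can produce wrong values for a listed endpoint. It is worth correcting before sampling, since last-dose time is easy to ask for at the draw and harder to recover later.

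**What to change.** 1. Add the date and time of the last ribociclib dose to Table 10.2 and to the PK form, asked at each draw, with the pill diary as back-up.
2. In Section 10.5, define steady-state C_trough as the on-treatment samples (C1D8, C1D15, C2D8, C2D15) drawn within a stated window after the recorded dose. A window of 20 to 28 h holds the timing error to about +9% / -8%.
3. Keep out-of-window on-treatment samples in a sensitivity analysis, either multiplied by 2^((t - 24)/32) to bring them to 24 h, or with time since dose as a covariate. At 14 h, a correction made with 32 h when the true half-life is 24 or 48 h leaves 1.335/1.242 = 1.07 or 1.155/1.242 = 0.93, an error of about 7% either way instead of 24%.
4. Where feasible, book the draw close to 24 h after the patient's usual dose time.

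**Cost.** One form field and a few sentences in Section 10.5. The real downside is lost samples: a strict window could exclude every evening doser. At an assumed share of 20% to 50%, that is 8 to 20 of 40 patients, selected by dosing habit. The time-adjusted analysis is needed for that reason. No change to dosing is proposed.
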